17.3. TYMPANOMETRY

Tympanometry assessments will be listed and tabulated for the right and left ear by treatment based on the Normal or Abnormal Tympanograms assessments. Tympanogram overall result will be derived programmatically as Normal for Type A assessments and will be derived as Abnormal for Type B or Type C assessments. The frequency of tympanogram results as Normal and Abnormal will be presented with the corresponding percentages for each ear, left and right, by treatment.

A shift table will be provided presenting the incidence of changes from baseline assessment to postbaseline assessments for the Tympanogram assessment as Normal or Abnormal for each ear by treatment along with the corresponding 95% CIs.

17.4. NASAL AND EPIPHARYNX ENDOSCOPY

All results from Nasal and Epipharynx Endoscopy for Normal or Abnormal appearance will be listed including the length of nasal cavity (defined as the distance from the tip of the nose to the entry point of the Eustachian tube) for both the left and right nare. The frequency of results (Normal or Abnormal) for each assessment will be tabulated by treatment and will be presented along with the corresponding percentages.

A shift table presenting the incidence of changes in overall result from baseline to each post-baseline assessment will be tabulated by treatment and for each ear (left and right), including the corresponding 95% CIs.

Results from Epipharynx Endoscopy (Normal and Abnormal) will be listed and tabulated similarly as described above for the right and left ear.

Document: Statistical Analysis Plan
Author: [REDACTED]

Version Number:
Version Date: 03APR2019

2.0

17.5. OLFACTORY TEST (UPSTIT)

The date and time of administration of the UPSIT test will be listed along with the test scores. A total UPSIT score of <35 is abnormal for females and a total score <34 is abnormal for males. Based on this criterion the Olfactory diagnosis, recorded on the CRF as Normal or Abnormal, will be included in the listing. A shift table indicating change in diagnosis from baseline to all postbaseline assessments will include the incidence as well as the corresponding 95% CI. Changes from Normal to Abnormal will also be recorded as Adverse Events and will be presented in the corresponding listings and summaries as described in Section 17.1.

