5.2 Exclusion Criteria

Subjects are excluded from the study if any of the following criteria apply:

1. History or presence of significant medical condition or a clinically significant abnormal finding, as determined by the Investigator. This includes study screening results from:
 - Medical history
 - Physical examination
 - ENT examination (ear history, otoscopy, tympanogram, nose and epipharynx endoscopy)
 - University of Pennsylvania Smell Inventory Test (UPSIT) olfactory test
 - Audiology pure tone hearing test
 - ECG
 - Vital signs measurements
 - Clinical laboratory tests
2. Presence of a clinically significant abnormal olfactory test finding at Screening defined as a total UPSIT score <35 (for females) and <34 (for males).
3. Current diagnosis of Sleep Apnea.
4. Clinically significant ear disorder/disease currently or within 6 weeks prior to Screening.
5. History of tympanostomy tubes in one or both ears within 1 year prior to Screening.
6. Upper respiratory tract infection or pharyngitis currently or within 6 weeks prior to Screening.
7. Allergy or sinus conditions (eg, sinusitis, non-specific nasal inflammation) currently or within 6 weeks prior to Screening.
8. Clinically relevant blockage of one or both nasal passages, in the Investigator's opinion.
9. Gastroesophageal reflux disease currently or within 6 weeks prior to Screening.
10. Smoker (eg, cigarettes, vapor) or tobacco or nicotine use within the last 48 weeks prior to Screening and positive urine cotinine test results at Screening or Day -1 prior to randomization.
11. Females with positive urine pregnancy results at Screening or Day -1 prior to randomization.
12. Females who are nursing or planning a pregnancy during the study.
13. Females of childbearing potential who are not willing to use an acceptable method of contraception during the study (see [Appendix 6](#)).

14. Symptomatic herpes zoster within 12 weeks prior to Screening.
15. Lymphoma, leukemia or any malignancy within the past 5 years except for basal cell or squamous epithelial carcinomas of the skin that have been resected with no evidence of metastatic disease for 3 years.
16. Breast cancer within the past 10 years.
17. Live vaccine within 30 days prior to Screening, or plans to receive such vaccines during the study.
18. Evidence of craniofacial anomalies (eg, cleft palate, Down's Syndrome).

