8.2.8 Olfactory Test

An olfactory test, UPSIT, will be performed at the Screening (Day -28 to Day -1) visit to ensure that a subject does not have a clinically significant condition or a condition that may pose an unacceptable safety risk for participation in the study. At the Day 8 and Day 14 visits, an olfactory test will be performed to assess for abnormal olfactory function after the dosing period. If abnormal findings are present at the Day 14 visit, then an additional olfactory test will be performed at the Day 21 study exit visit.

The UPSIT test consists of 4 booklets containing 10 odorants apiece, 1 odorant per page. The stimuli are embedded in 1 μ m to 50 μ m diameter microencapsulated crystals located on brown strips at the bottom of each page. Above each odorant strip is a multiple-choice question with 4 alternative responses for each item. For example, 1 of the items reads, “This odor smells most like: a) chocolate; b) banana; c) onion; or d) fruit punch.” The response “banana” is correct in this case. The subject is required to answer 1 of the 4 alternatives, even if no smell is perceived (ie, the test is forced-choice). This helps to encourage the subject to sample each odorant and provides a basis for the detection of malingering. To ensure uniformity in test administration, the test booklets should be administered in chronologic order, eg, booklet 1, booklet 2, etc. (Doty 1984). A total UPSIT score of <35 is abnormal for females and a total score <34 is abnormal for males. In this study we intend to determine if there is any change from ‘normal’ (at baseline) to ‘abnormal’ post-treatment. If such a change occurs it will be captured as an AE. The severity of the AE will be assessed as per the resulting ‘olfactory diagnosis’ in the following table:

Test Score	Olfactory Diagnosis
00-05	Probable Malingering
06-18	Total Anosmia
19-25	Severe Microsmia
26-29	Moderate Microsmia (males)
26-30	Moderate Microsmia (females)
30-33	Mild Microsmia (males)
31-34	Mild Microsmia (females)
34-40	Normosmia (males)
35-40	Normosmia (females)

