- f To be performed at Screening only (see Protocol Table 8, Appendix 3).
- g Includes general appearance, overall status of the skin, head, neck, trunk, eyes, heart and lungs (eg, breathing sounds), abdomen, extremities, lymph nodes. Height and weight are recorded only at the Screening visit.
- h Vital signs include blood pressure, respiratory rate, pulse rate, and body temperature.
- i A single 12-lead ECG will be collected for screening purposes. For subjects in Cohort A, a single 12-lead ECG will be collected on Day 1 prior to the first dose and on the study exit visit (Day 21). For subjects in Cohort B, triplicate ECGs will be collected on Day 1: 30 and 60 minutes prior to the first dose, Day 14: 30 minutes prior to the last dose and 5, 20, 35, 50 minutes following the last dose on Day 14. In cases where ECG and PK sampling overlap, ECGs should be collected first, to ensure that PK samples are collected at the scheduled time point.
- j Otoscopy involves ear endoscopy, taking a picture of the tympanic membrane and assessing if there are any abnormal findings.
- k Nasal endoscopy will include a measurement of nasal cavity length (in mm) at the Screening visit only. For all other scheduled assessments, the nasal and epipharynx endoscopy assessment should be done prior to the first dose of the day.
- l Includes hematology, clinical chemistry, coagulation and urinalysis (see Protocol Table 8, Appendix 3).
- m At Screening, a total UPSIT score of ≥ 35 (for females) and a total UPSIT score of ≥ 34 (for males) is required to meet study enrollment criteria.
- n To be collected at the Day 21 study exit visit only if abnormal at the Day 14 visit. Abnormal is defined as UPSIT score < 35 (for females) and < 34 (for males) (see Protocol Section 8.2.8).
- o Audiology pure tone hearing test if abnormal in either ear at Day 14 visit. Abnormal defined as > 20 dB worsening from baseline at Day 14 visit (See Protocol reference Rosenfeld et al, 2004). Tympanometry is performed along with the Audiology pure tone hearing test so if the subject requires a hearing test at this visit, tympanometry will also be performed.
- p Audiology pure tone hearing test and tympanometry not required if subjects drops out before Day 14, but if they drop out after Day 14 and had an abnormal test result at Day 14 visit, then every effort should be made to have the patient complete these assessments at the EaT visit.

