7.5. BASELINE

Baseline is defined as the last scheduled non-missing measurement taken prior to dosing and will

Document: Statistical Analysis Plan
Author: [REDACTED]

Version Number:
Version Date:

2.0
03APR2019

correspond to: Screening assessment for clinical laboratory; Day -1 assessment for Vital Signs; Day 1 pre-dose assessment for ECG in Cohort A, and the average of the mean triplicate ECG assessments at Day 1, 60 minutes pre-dose and Day 1, 30 minutes pre-dose for ECG in Cohort B; Screening assessment for Physical Examination; Day -1 assessment for Otoscopy, Tympanometry, and Nasal and Epipharynx Endoscopy ; and Screening assessment for University of Pennsylvania Smell Inventory Test (UPSIT) Olfactory test, and Audiology Pure Tone hearing test. However, if a subject is missing the planned baseline collection then the last non-missing evaluation prior to dosing (scheduled or unscheduled), if available, will become the baseline value.

For PK assessments, baseline serum concentration is defined as the mean of the two predose serum concentrations observed in samples collected on Day 1 prior to the first dose. If one predose sample is missing, the other Day 1 predose concentration will be used for baseline correction.

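### SAP 17.5 tabulates UPSIT only as a Normal/Abnormal shift at the entry cut-off, so within-normal falls and the size of any fall are not summarised

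*SAP*

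**What the plan says.** - **Scale.** Protocol 8.2.8: "The UPSIT test consists of 4 booklets containing 10 odorants apiece, 1 odorant per page". The total therefore runs from 0 to 40.
- **Entry.** SAP 4.2, footnote m: "At Screening, a total UPSIT score of ≥ 35 (for females) and a total UPSIT score of ≥ 34 (for males) is required" for enrolment. Protocol 5.2 excludes subjects below the same values.
- **Baseline.** SAP 7.5 sets it as the "Screening assessment for University of Pennsylvania Smell Inventory Test (UPSIT) Olfactory test", which is the score that qualified the subject.
- **Analysis.** SAP 17.5 lists individual scores and applies this rule: "A total UPSIT score of <35 is abnormal for females and a total score <34 is abnormal for males". The only tabulation it names is "A shift table indicating change in diagnosis from baseline to all postbaseline assessments", with incidence and a 95% CI.
- **Adverse events.** Protocol 8.2.8, on a change from normal to abnormal: "If such a change occurs it will be captured as an AE". No minimum change is required. Severity follows the diagnosis band of the resulting score.
- **Timing.** UPSIT is repeated on Day 8 and Day 14, and at the Day 21 exit visit only if Day 14 was abnormal.
- **Other measures.** SAP 17.7 to 17.9 each name observed values and change from baseline, for laboratory tests, ECG and vital signs. Section 17.5 does not. SAP 7.1 (descriptive statistics) and 7.7 (change from baseline) are general rules that do not name UPSIT.

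**The concern.** Smell is an obvious local safety question for a product sprayed into the nose 3 times a day, and UPSIT is among the primary endpoints in SAP 3.1. A two-category table at the entry cut-off discards most of the score. Whether a fall counts depends mainly on how far above the cut-off the subject started. A shared, moderate fall on active treatment would show only in subjects who began close to the line, while ordinary retest variation in those same subjects is recorded as an adverse event. With 12 subjects per active dose and 6 on pooled placebo, a reader of the tables could not tell one pattern from the other.

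**Working it through.** The plan states no power, effect size or precision figure for UPSIT, so there is none to reproduce. Group sizes follow from 15 per cohort at 4:1: 15 × 4/5 = 12 active and 15 × 1/5 = 3 placebo, giving 6 placebo when pooled.

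**1. Arithmetic on the cut-offs (no assumptions)**

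| | Females | Males |
|---|---|---|
| Lowest normal score | 35 | 34 |
| Largest fall that stays Normal | 40 − 35 = 5 | 40 − 34 = 6 |
| Smallest fall that always crosses | 6 | 7 |
| Smallest fall that can be an AE | 35 to 34 = 1 | 34 to 33 = 1 |

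A uniform 3-point fall in females crosses from baselines 35, 36 and 37 (to 32, 33, 34) but not from 38, 39 and 40 (to 35, 36, 37).

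**2. Size of a fall that crosses**

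The shift table puts 35 to 34 and 40 to 10 in the same cell. The Protocol 8.2.8 bands separate some such cases, but they grade where the subject ends and not how far the subject fell:
- Males, mild band 30 to 33: 34 to 33 (1 point) and 40 to 30 (10 points) are both mild.
- Females, mild band 31 to 34: 35 to 34 (1 point) and 40 to 31 (9 points) are both mild.

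SAP 17.1 takes severity from Protocol Appendix 4, which grades by interference with daily activities, and does not cite the 8.2.8 bands.

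**3. Chance crossings with no drug effect (all inputs assumed)**

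The documents give no retest error and no score distribution. Assume a true score that is normal with mean 36 to 38 and SD 1.5, and an independent retest SD of 0.5 to 2. Round scores, cap them at 40, and require a qualifying Screening score. The simulated chance of an abnormal result on Day 8 or Day 14 is then:

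| Cut-off | Mean 38, retest SD 0.5 | Mean 37, retest SD 1 | Mean 36, retest SD 2 |
|---|---|---|---|
| Female (<35) | 1.0% | 8.6% | 35.4% |
| Male (<34) | 0.2% | 3.2% | 22.4% |

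At 8.6%, the expected number is 12 × 0.086 = 1.0 chance event per active group of 12.

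**4. Precision of the shift table**

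The SAP does not name the CI method; exact (Clopper-Pearson) limits are assumed. With no events the upper limit is 1 − 0.025^(1/n).
- 0/12: 1 − 0.025^(1/12) = 26.5%.
- 0/6 pooled placebo: 1 − 0.025^(1/6) = 45.9%.

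**5. Precision of a mean change, if the SD of change is 2 points (assumed)**
- One group of 12: t(0.975, 11)/√12 = 0.635, and 0.635 × 2 = 1.3 points either side.
- Active minus pooled placebo, 12 vs 6: 2.12 × 2 × √(1/12 + 1/6) = 2.1 points either side.

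**The case against.** A reader might infer that large losses of smell would be invisible under this plan. The documents do not support that. A fall of 6 or more (females) or 7 or more (males) crosses from any eligible baseline, enters the shift table and becomes an adverse event. Individual scores are listed, and an abnormal Day 14 result triggers a Day 21 retest.

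Nor can it be said that the table could not show a uniform moderate loss. Assume males with baseline mean 37 to 38, SD 1.5 to 1.2 and noise SD 1. A true 3-point loss in everyone then flips about 37% to 17% at one visit, so the chance of at least one flip among 12 runs from 1 − 0.83^12 = 89% to 1 − 0.63^12 = 99.6%. The signal is weakened, not lost.

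Three further points stand in part:
- The protocol's stated aim for UPSIT is a change from normal to abnormal, and the shift table serves it. That is a reason to keep the table, not a reason to omit the score.
- SAP 7.1 and 7.7 could be read to cover UPSIT, SAP 7.3 names it among variables with derivations, and the output shells are not available. A score table may therefore be intended. Because 17.7 to 17.9 state such summaries and 17.5 does not, one sentence would settle it.
- A change table does not cure regression to the mean from a selected baseline, and the adverse-event rule stays in force. Both are true. Randomised placebo subjects share the same regression, so active change should be read against placebo change and not against zero.

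**Conclusion.** The point holds as a gap in what is summarised. As written, SAP 17.5 leaves within-normal falls of up to 5 points (females) or 6 (males) to the listings, makes a 1-point fall at the cut-off an adverse event, and gives no summary of how far subjects fell once they crossed. The severity bands do not fill that gap, because they grade the final score. These statements follow from the cut-offs alone.

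How often chance alone would produce a crossing is not established. The range of about 0.2% to 35% rests wholly on assumed means, spread and retest error, and the documents cannot narrow it.

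**What to change.** In SAP 17.5:
- Add observed total UPSIT score and change from baseline by treatment group, with placebo pooled, at Day 8 and Day 14 (n, mean, SD, median, minimum, maximum). Day 21 can stay in listings, since it is tested only after an abnormal Day 14 result.
- Show baseline score and change beside each UPSIT-derived adverse event.
- Keep the shift table.
- State that active change is to be read against placebo change.

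A between-group confidence interval is optional. SAP 17 plans no treatment comparisons for safety data unless a section specifies one, and the interval would be wide, about ±2.1 points under the assumption above.

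The cost is one table and two listing columns from scores already collected. The change does not remove threshold-crossing adverse events or regression to the mean within an arm; it lets a reader judge their size.

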17.6. AUDILOGY PURE TONE HEARING TEST

The date and time of Audiology Pure Tone hearing test will be listed including the results from each assessment at all tested frequencies. Results from Speech Audiometry and Screening Reflex Threshold for both ears will be listed. The interpretation of the results indicating the extent of hearing loss will also be indicated. Frequency counts and percentages for each category of hearing loss will be tabulated by treatment for all visits.

A shift table indicating change in overall hearing loss from baseline to all postbaseline assessments will include the incidences as well as the corresponding 95% CI.

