8.2.9 Audiology Pure Tone Hearing Test

An audiology pure tone hearing test will be performed at the Screening (Day -28 to Day -1) visit to ensure that a subject does not have clinically significant abnormal hearing. Average pure tone hearing loss at 4 frequencies (500, 1000, 2000 and 4000 Hz) ranges from normal hearing to moderate hearing loss (0-55 dB) will be tested. The 50th percentile is about 25 dB hearing level (HL). Average pure tone audiometry will be performed as per the audiology testing template in [Appendix 10](#). The hearing test should be performed in a quiet environment, preferably a separate closed or sound-proofed area set aside specifically for that purpose. Comprehensive audiologic evaluation is recommended for anyone who fails the pure tone hearing test. Audiologic assessment includes evaluating air-conduction and bone-conduction thresholds for pure tones, speech detection or speech recognition thresholds, and measurements of speech understanding, if possible ([Rosenfeld et al, 2004](#)).

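### SAP 17.6 tabulates hearing only by category, with no summary of change in dB and no count of subjects meeting the >20 dB worsening rule that triggers the Day 21 retest

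*SAP*

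**What the plan says.** The audiology test is named in the primary safety endpoint (Protocol 3.0; SAP 3.1). Its baseline is the Screening assessment (SAP 7.5).

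SAP 17.6 plans three outputs:
- a listing, in which results "will be listed including the results from each assessment at all tested frequencies";
- a frequency table: "Frequency counts and percentages for each category of hearing loss will be tabulated by treatment for all visits";
- a shift table: "A shift table indicating change in overall hearing loss from baseline to all postbaseline assessments", with incidences and 95% CIs.

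The abnormality rule stands elsewhere, in footnote o to the schedule (Protocol 1.3, repeated in SAP 4.2). The Day 21 test is governed by "Audiology pure tone hearing test if abnormal in either ear at Day 14 visit", and the footnote continues "Abnormal defined as > 20 dB worsening from baseline at Day 14 visit". SAP 17.6 does not refer to it.

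On measurement, Protocol 8.2.9 says only: "Average pure tone hearing loss at 4 frequencies (500, 1000, 2000 and 4000 Hz) ranges from normal hearing to moderate hearing loss (0-55 dB"). Neither document gives limits for the hearing-loss categories, says how two ears become one overall result, or says whether the >20 dB rule applies to a single frequency or to the average.

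**The concern.** A category shift depends on where the ear starts. A small change near a boundary counts, and a larger change inside a wide band does not. The >20 dB rule measures change directly, and it is the only post-treatment definition of an abnormal hearing test in the documents. As written, the tables by treatment could record a shift for a subject who did not meet the rule, and in some circumstances no shift for one who did.

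The SAP treats comparable measures differently. Section 17.5 uses the protocol's UPSIT cut-offs, 17.8.1 classifies QTcF increases of >30 and >60 msec, and 17.7, 17.8 and 17.9 summarise change from baseline for laboratory tests, ECG and vital signs. SAP 7.7 defines change from baseline for quantitative measurements in general. Audiometric thresholds are quantitative and have a change criterion, but 17.6 summarises neither the change nor the criterion. With a drug aimed at the Eustachian tube and groups of 12, 12 and 6, a reader will want that count by treatment without having to assemble it from listings.

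**Working it through.** The plan states no figure to reproduce. The check is whether the category shift and the >20 dB rule can disagree, and in which direction.

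**Inputs.** From the documents: the >20 dB rule (footnote o), the 0-55 dB range and the four frequencies 500, 1000, 2000 and 4000 Hz (Protocol 8.2.9), and group sizes of 12 per dose and 3 + 3 = 6 pooled placebo (SAP Table 1 and 7.2). Assumed, because the documents are silent: categories are numeric bands of the four-frequency average, with several trial sets of upper limits.

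**Step 1. Enumerate.** Take every pair of whole-dB averages from 0 to 55 in which the later value is worse: 56 × 55 / 2 = 1,540 pairs. For each, compare worsening >20 dB with a move to a worse category. The counts show what is possible. They are not probabilities.

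| Assumed upper limits (dB) | Shift, but not >20 dB | >20 dB, but no shift |
|---|---|---|
| 15, 25, 40 | 535 | 0 |
| 20, 40 | 405 | 0 |
| 20, 35 | 405 | 0 |
| 25, 40 | 390 | 15 |
| 25 only | 210 | 60 |

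**Step 2. Shift without >20 dB.** This occurs under every set. With a limit at 25 dB, an ear going from 24 to 27 dB shifts on a 3 dB change.

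**Step 3. >20 dB of the average without a shift.** In a band from L to U, the largest worsening without a shift is U − L, so a miss needs U − L > 20.
- Normal band 0-15: at most 15 dB, no miss.
- Normal band 0-20: at most 20 dB, which is not >20, no miss.
- Normal band 0-25: at most 25 dB. Baselines of 0 to 4 dB give 5 + 4 + 3 + 2 + 1 = 15 missed pairs, such as 0 to 21 dB.

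The other 45 of the 60 pairs in the last row start at 26-34 dB, inside an assumed band of 26-55 dB.

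**Step 4. If the rule is read per frequency.** A loss of d dB at one of four frequencies moves the average by d/4: 25/4 = 6.25 dB and 40/4 = 10 dB. A subject can then exceed 20 dB at one frequency and stay in the same category under any of the sets above.

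**Step 5. What the proposed count would show.** Exact 95% intervals: with no events the upper limit is 1 − 0.025^(1/n), giving 0-26.5% for 0/12, 0-45.9% for 0/6 and 0-14.2% for 0/24 (all active). One event in 12 gives 0.2-38.5%.

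**The case against.** Several points can fairly be made for the plan as it stands.

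- **The rule is a retest trigger.** It appears only in schedule footnotes. Protocol 9.4.3 leaves the audiology summary to what is appropriate, and SAP 17.6 supplies one. This stands: a reader might infer that a promised analysis is missing, and the documents do not support that.
- **More than a shift table is planned.** Category frequencies by visit and listings by frequency are there too. This stands, but both tables are category-based and a listing gives no rate by treatment.
- **Day 21 numbers are a proxy.** Only subjects abnormal at Day 14 are retested, so the number tested at Study Exit approximates the number meeting the rule. The proxy is indirect: a retest can be missed, and SAP 7.6 merges early-termination results into Study Exit.
- **Adverse events are tabulated.** Protocol 7.0 and Appendix 4 bring in findings judged clinically relevant or significant. That depends on the investigator's judgement. Hearing has no automatic rule like the one for UPSIT in Protocol 8.2.8.
- **The categories may be a clinician's reading.** SAP 17.6 mentions an interpretation of the extent of loss, and the template in Protocol Appendix 10 has a findings field. If so, the band arithmetic does not apply directly. The lack of a stated link between category and rule remains.
- **The table shells** cited in SAP 9 are not among the documents, so a shell with this count cannot be excluded. The SAP text should still specify it.

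**Conclusion.** The point holds as an improvement to the analysis. The SAP text plans no summary of change in dB and no count of subjects with >20 dB worsening, although that rule decides who is retested.

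The directions of disagreement differ in strength. A shift without >20 dB worsening is possible under any numeric cut-points. A >20 dB worsening of the average that goes unseen requires a category wider than 20 dB, for example an assumed normal limit of 25 dB; with limits of 15 or 20 dB for normal and no wider band above, it cannot happen. A >20 dB loss at one frequency can go unseen under every set tried, provided the categories rest on the four-frequency average, which the documents do not state.

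A reader might infer that the shift table will generally hide losses that meet the rule. The documents do not support that, because they give no category limits. No between-group test or sample-size figure is affected.

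**What to change.** In SAP 17.6 add one table by treatment:

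- (a) observed value and change from baseline in dB, per ear, at Day 14, for the 500-4000 Hz average;
- (b) n/N, percentage and exact 95% CI of subjects with >20 dB worsening from baseline in either ear.

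State whether the rule actually used for the retest is per frequency or on the average. If this is unresolved, show (b) both ways, because a count on the average alone misses the single-frequency losses in Step 4. Define the hearing-loss categories and how the two ears form the overall result. Keep the category tables as supportive, and label Day 21 results as coming only from subjects retested.

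The cost is one extra descriptive table from thresholds already recorded. Its intervals will be wide at 12, 12 and 6 subjects and should be read as description only.
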